2	Reported vial size	
Reported vial size in the following categories (categorical):
 
 • Unknown vial – IP dose • 44 milligram (mg)/1.1 milliliter (mL) • 76mg/1.9mL • Missing dose/unknown dose 
For the exploratory cohort of teclistamab patients the reported vial size (categorical):
 
 • Unknown vial – IP dose • 30mg/3mL • 153mg/7mL 
Missing dose/unknown dose
	
Index date to the end of follow-up
 
Index date
 
Step-Up Dosing Period
 
Maintenance Periods
 
See Section 9.7.2 for more information on the assessment periods and censoring criteria

2	Patients with 2 or more administrations	Proportion of patients with 2 or more administrations of elranatamab during the assessment period	
Index date to the end of follow-up
 
Step-Up Dosing Period
 
Maintenance Periods
 
See Section 9.7.2 for more information on the assessment periods and censoring criteria

2	Average time between elranatamab claims	Sum of the days between claims for the index drug (continuous) divided by the total number of administrations -1 reported among patients with 2 or more administrations	Index date to the end of follow-up Step-Up Dosing Period Maintenance Periods See Section 9.7.2 for more information on the assessment periods and censoring criteria
2	Number of elranatamab claims	Total number of IP, non-IP, and pharmacy claims of the index drug during the time period based on vial size (continuous)	Index date to the end of follow-up Step-Up Dosing Period Maintenance Periods See Section 9.7.2 for more information on the assessment periods and censoring criteria
3	RAI	The ratio of the actual administrations received divided by the expected number of administrations (continuous) See Section 9.7.3 for more details.	Index date to the last administration of the index drug Step-Up Dosing Period Maintenance Periods See Section 9.7.2 for more information on the assessment periods and Section 9.7.3 for censoring criteria
3	Duration on treatment	Time in days between first and last treatment administration for the index treatment (continuous)	Index date to the end of follow-up See Section 9.7.2 for censoring criteria

3	TTD	Time in months from first administration until last administration prior to treatment discontinuation (continuous). Treatment discontinuation is defined as an 8-week gap in elranatamab (or for the exploratory analysis, teclistamab therapy), next treatment after index treatment (CAR-T, BsABs, bendamustine or belantamab), or death.	Index date to the end of follow-up. Follow-up will be defined based on the censoring criteria described in Section 9.7.4
Health care resource utilization and costs			
4	All-cause IP visits	Medical claim for IP (non-ED) visit (dichotomous)	180 days prior to index date to 1 day prior to index date
		Number of IP (non-ED) visits (continuous)	Step-Up Dosing Period Index date to end of follow-up. Follow-up will be defined two ways to account for gaps in elranatamab use. See Section 9.7.5 for censoring criteria
4	IP visits from the IP table	Medical claim for IP (non-ED) visit sourced from the IP table (dichotomous)	180 days prior to index date to 1 day prior to index date
		Number of IP (non-ED) visits sourced from the IP table (continuous)	Step-Up Dosing Period Index date to end of follow-up. Follow-up will be defined two ways to account for gaps in elranatamab use. See Section 9.7.5 for censoring criteria
4	IP visits from the Non-IP table	Medical claim for IP (non-ED) visit sourced from the Non-IP table where place of service indicates an IP setting (dichotomous)	180 days prior to index date to 1 day prior to index date

		Number of IP (non-ED) visits sourced from the IP table place of service indicates an IP setting (continuous)	Step-Up Dosing Period Index date to end of follow-up. Follow-up will be defined two ways to account for gaps in elranatamab use. See Section 9.7.5 for censoring criteria
4	All-cause OP visits	Medical claim for non-IP/non-ED visit (dichotomous)	180 days prior to index date to 1 day prior to index date
		Number of non-IP/non-ED visits (continuous)	Step-Up Dosing Period Index date to end of follow-up. Follow-up will be defined two ways to account for gaps in elranatamab use. See Section 9.7.5 for censoring criteria
4	All-cause ED visits	Medical claim for ED visit (dichotomous)	180 days prior to index date to 1 day prior to index date
		Number of ED visits (continuous)	Step-Up Dosing Period Index date to end of follow-up. Follow-up will be defined two ways to account for gaps in elranatamab use. See Section 9.7.5 for censoring criteria
4	All-cause pharmacy claims	Pharmacy claim (dichotomous)	

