1	Time since MM diagnosis	Time (in months) from first MM diagnosis to index date (continuous)	MM diagnosis to index date

Objective	Variable	Definition	Assessment Period(s)
1	Triple class exposed	
Medical claim in the IP, Non-IP or pharmacy setting with an NDC, HCPCS, Current Procedural Terminology (CPT), generic name, or ICD-10 procedure code for all the following therapies in the IP, non-IP, or pharmacy setting (dichotomous)¹⁶:
 
 • ≥ 1 claim for PIs (see generic names below) • ≥ 1 claim for IMiDs (see generic names below) • ≥ 1 claim for CD38 mAbs (generic names: daratumumab, isatuximab) 	MM diagnosis to 1 day prior to index date
1	Penta-drug exposed	
Medical claims with an NDC, HCPCS, CPT, generic name, or ICD-10 procedure codes in the IP, non-IP or pharmacy setting for all of the following therapies (dichotomous)¹⁶:
 
 • ≥ 2 distinct claims for PIs (see generic names below) • ≥ 2 distinct claims for IMiDs (see generic names below) • ≥ 1 claim for CD38 mAbs (generic names: daratumumab, isatuximab) 	MM diagnosis to 1 day prior to index date
1	Hematopoietic Stem Cell Transplantation ¹	
Medical claim with an HCPCS, CPT, or ICD-10 code for hematopoietic stem cell transplantation in the IP, non-IP setting (dichotomous)
	
MM diagnosis to 1 day prior to index date
 
Index date to the end of follow-up

1	BCMA-directed therapy ¹	
Medical claim with an NDC, HCPCS CPT, generic name or ICD-10 procedure code in the IP, non-IP, or pharmacy setting for idecabtagene vicleucel, ciltacabtagene autoleucel, or belantamab (dichotomous)
	
MM diagnosis to 1 day prior to index date
 
Index date to the end of follow-up

1	CAR-T ¹	
Medical claim with an NDC, HCPCS, generic name or CPT code in the IP, non-IP, or pharmacy setting for idecabtagene vicleucel or
	
MM diagnosis to 1 day prior to index date

Objective	Variable	Definition	Assessment Period(s)
		ciltacabtagene autoleucel (dichotomous)	Index date to the end of follow-up
1	Talquetamab ¹	Medical claim with an NDC, HCPCS, generic name or CPT code in the IP, non-IP, or pharmacy setting for talquetamab (dichotomous)	MM diagnosis to 1 day prior to index date Index date to the end of follow-up

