1	PIs ¹	Medical claim with an NDC, HCPCS, generic name or CPT code in the IP, non-IP, or pharmacy setting for bortezomib, carfilzomib, or ixazomib (dichotomous)	MM diagnosis to 1 day prior to index date Index date to the end of follow-up
1	IMiDs ¹	Medical claim with an NDC code or generic name in the non-IP or pharmacy setting for lenalidomide, thalidomide, or pomalidomide (dichotomous)	MM diagnosis to 1 day prior to index date Index date to the end of follow-up
1	Steroids ¹	Medical claim with an NDC, HCPCS, generic name or CPT code in the IP, non-IP, or pharmacy setting for dexamethasone, methylprednisolone, prednisone, or prednisolone (dichotomous)	MM diagnosis to 1 day prior to index date Index date to the end of follow-up
1	MAbs ¹	Medical claim with an NDC, HCPCS, generic name or CPT code in the IP, non-IP, or pharmacy setting for daratumumab, isatuximab, or elotuzumab (dichotomous)	MM diagnosis to 1 day prior to index date Index date to the end of follow-up
1	Chemotherapies ¹	Medical claim with an NDC, HCPCS, generic name or CPT code in the IP, non-IP, or pharmacy setting for	MM diagnosis to 1 day prior to index date

Objective	Variable	Definition	Assessment Period(s)
		doxorubicin hydrochloride, melphalan, bendamustine, cyclophosphamide, etoposide, or cisplatin (dichotomous)	Index date to the end of follow-up
1	Small molecule inhibitors ¹	Medical claim with an NDC, HCPCS, generic name or CPT code in the IP, non-IP, or pharmacy setting for venetoclax (dichotomous)	MM diagnosis to 1 day before index date Index date to the end of follow-up
1	Nuclear export inhibitors ¹	Medical claim with an NDC, HCPCS, generic name or CPT code in the IP, non-IP, or pharmacy setting for selinexor (dichotomous)	MM diagnosis to 1 day before index date Index date to the end of follow-up
1	Antivirals ¹	Medical claim with an NDC, HCPCS, generic name or CPT code in the IP, non-IP, or pharmacy setting for antiviral medications (dichotomous)	14 days prior to index date to 1 day prior to index date Index date to the end of follow-up
1	Antibiotics ¹	Medical claim with an NDC, HCPCS, generic name or CPT code in the IP, non-IP, or pharmacy setting for antibiotic medications (dichotomous)	14 days prior to index date to 1 day prior to index date Index date to the end of follow-up

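### The penta-drug flag in Table 2 counts two claims, not two different drugs, for PIs and for IMiDs, so a patient with only three or four drugs can qualify

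*Protocol*

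**What the plan says.** Protocol section 9.3, Table 2, lists two neighbouring prior-treatment flags for Objective 1. Both are assessed from MM diagnosis to the day before index.

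- **Triple class exposed:** at least "1 claim for PIs (see generic names below", at least one claim for IMiDs and at least one for anti-CD38 antibodies.
- **Penta-drug exposed:** at least "2 distinct claims for PIs (see generic names below", at least "2 distinct claims for IMiDs (see generic names below", and at least "1 claim for CD38 mAbs (generic names: daratumumab, isatuximab".

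The pointer to generic names leads to the class rows further down Table 2. The PI row covers "bortezomib, carfilzomib, or ixazomib (dichotomous". The IMiD row covers claims in the non-inpatient or "pharmacy setting for lenalidomide, thalidomide, or pomalidomide (dichotomous". Both are yes/no at class level.

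Annex 2 lists codes for PIs, IMiDs and CD38 mAbs by class and has no entry for penta-drug exposure. Section 9.8 (Quality Control) says that measures will be coded from the codes and algorithms in the protocol and that the protocol will be followed strictly.

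**The concern.** The name of the variable says five drugs, and 2 + 2 + 1 gives five only if the counts are of drugs. The row counts claims. PIs and IMiDs are given or refilled repeatedly, and the look-back can reach to 01 January 2016, so one agent can supply both claims in its class. A programmer who follows the row to the letter would flag patients who have had three or four drugs.

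At stake is one descriptive figure under primary Objective 1. It matters more than its single row suggests. The inclusion criteria (section 9.2.1) ask only for an MM diagnosis, with no required prior lines or drug classes. Table 2 has no count of prior lines, and it reports PIs and IMiDs only as yes/no. The penta-drug flag is therefore the one planned row that could show depth of exposure within those two classes. A reader could not recover the number of agents from the other rows.

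**Working it through.** The plan states no figure to reproduce. The check applies the written rule to the drugs that the plan lists.

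**Inputs (Table 2).** Three PIs (bortezomib, carfilzomib, ixazomib), three IMiDs (lenalidomide, thalidomide, pomalidomide) and two anti-CD38 antibodies (daratumumab, isatuximab). Claim thresholds are 2, 2 and 1 for the penta-drug flag, and 1, 1 and 1 for the triple-class flag.

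**1. Fewest drugs that satisfy each rule.**
- Written rule: 1 PI + 1 IMiD + 1 anti-CD38 = 3. Two bortezomib, two lenalidomide and one daratumumab claim qualify.
- Distinct-agent rule: 2 + 2 + 1 = 5.

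**2. Difference from the triple-class flag.** The classes, the window and the anti-CD38 threshold are the same. A triple-class patient fails the penta-drug rule only with exactly one PI claim or exactly one IMiD claim.

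**3. Direction.** Each agent needs its own claim, so two different PIs imply at least two PI claims, and likewise for IMiDs. Every patient who meets the distinct-agent rule therefore meets the written rule. The reverse fails. On the same claims the written rule can only add patients.

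**4. Enumeration of drug combinations.** Assume that each drug received yields at least two claims.
- Non-empty sets of agents: (2³ − 1) × (2³ − 1) × (2² − 1) = 7 × 7 × 3 = 147. All 147 meet the written rule.
- With exactly three drugs: 3 × 3 × 2 = 18.
- With exactly four drugs: two PIs, one IMiD and one anti-CD38 give 3 × 3 × 2 = 18; one PI, two IMiDs and one anti-CD38 give 18; one PI, one IMiD and both anti-CD38 give 3 × 3 × 1 = 9. Total 45.
- Fewer than five drugs: 18 + 45 = 63. Five or more: 147 − 63 = 84.
- Distinct-agent rule: four sets of at least two PIs, four sets of at least two IMiDs, three anti-CD38 sets, so 4 × 4 × 3 = 48. None has fewer than five drugs.
- Added by the written rule: 147 − 48 = 99. Of these, 63 have fewer than five drugs. The other 84 − 48 = 36 have five or more but only one PI or only one IMiD (for example three PIs, one IMiD and one antibody).

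These are counts of possible combinations, not of patients.

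**5. Size in patients.** Let *t* be the share of the cohort that is triple-class exposed. Among those patients, let *a* be the share with at least two claims in both the PI and IMiD classes, and *b* the share with at least two agents in both. The excess in the reported percentage is *t* × (*a* − *b*), with *b* ≤ *a* by step 3. It ranges from 0 (every patient with repeat claims had changed agent in both classes) to *t* × *a* (none had). The protocol gives none of *t*, *a* or *b*, so no figure follows.

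**The case against.** The best defence is that the wording is ambiguous, not settled. The word distinct appears in the penta-drug row and not in the triple-class row above it. Two claims are already separate claims, so the word may have been meant as claims for distinct agents, and the row's name and its pointer to generic names favour that reading. The row also cites a source, and Annex 1 lists table shells. Neither is at hand, so what was actually programmed is unknown. This stands as a limit on what can be said about results. It does not rescue the text: no other place in the protocol requires different agents, and section 9.8 binds the programmer to the text.

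The second defence is that the flag is one row among many. Eligibility, censoring and outcome definitions do not use it, section 9.7 plans no formal comparison between groups, and OS and TTNT/D are exploratory. That also stands, and it keeps the severity down.

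Three stronger inferences are tempting, and the documents do not support them:
- **A large error stated in percentage points.** This needs patient shares that the protocol does not give.
- **A cohort that looks more heavily pretreated than it truly is.** Only 180 days of continuous closed-claims enrollment before index are required, so older PI and IMiD use may be missed or seen only once. That pulls observed exposure down. It affects both rules alike, so the comparison between rules holds, but the net error against true exposure is unknown.
- **Distorted survival or time-to-next-treatment results.** Those estimates do not depend on the flag. At most, a reader who uses it to place the cohort beside others would be misled about treatment history.

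**Conclusion.** The point holds for the definition as written. Table 2 lets a patient with three or four drugs be labelled penta-drug exposed and leaves the flag close in construction to the triple-class flag. Relative to a distinct-agent rule on the same claims, the written rule cannot understate penta-drug exposure, and it overstates it wherever a triple-class patient has at least two claims in both classes but has not received two different agents in both. This conclusion rests on the wording of the row, the name of the variable and its 2 + 2 + 1 structure. It does not rest on the cited source or on any assumed patient share. The two-claim threshold applies to PIs and IMiDs only, since anti-CD38 antibodies need one claim.

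Severity is moderate: a primary-objective descriptor does not measure what its name states, but no eligibility decision or computed outcome changes.

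**What to change.** Reword the Table 2 row to require, from MM diagnosis to one day before index, claims for:

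- at least two different PI generic names among bortezomib, carfilzomib and ixazomib;
- at least two different IMiD generic names among lenalidomide, thalidomide and pomalidomide;
- at least one anti-CD38 antibody (daratumumab or isatuximab).

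Split the Annex 2 PI and IMiD codes by agent, because they are now pooled by class although the generic names are listed. Rerun the flag for the elranatamab and teclistamab cohorts. If the program already counts distinct agents, only the text needs to change.

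The cost is one row of text, some code mapping and a rerun. The milestones after this protocol version include refreshes on 09 September and 20 December 2025 and a final report on 28 February 2026, so the change fits work already planned. If claims were counted until now, the reported share will fall or at most stay the same, and a note should explain the break from earlier refreshes.

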8. RESEARCH QUESTION AND OBJECTIVES

Research Question: What are the descriptive characteristics, treatment patterns, all cause/MM-related HCRU, safety and effectiveness of elranatamab therapy?

The study objectives are to:

Primary

- **Objective 1:** Describe the demographics, clinical history, and treatment history of patients in the study
- **Objective 2:** Describe the administration and treatment management of elranatamab
- **Objective 3:** Describe all-cause and MM-related HCRU and costs by place of service of patients in the study

Exploratory

- **Exploratory Objective 1:** Describe the tolerability and real-world safety of elranatamab
- **Exploratory Objective 2:** Describe the effectiveness of elranatamab in terms of TTNT/D and OS
- **Exploratory Objective 3:** In a separate cohort, replicate all objectives for patients with the same indication as elranatamab who initiated teclistamab

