9.2. Setting

This study will evaluate adult patients with RRMM who initiate elranatamab. Patients will enter (i.e., index) on the first observed elranatamab claim between 14 August 2023 and the end of data (defined as the latest data at the time of the specified analysis). Limited eligibility criteria will be applied.

Study Period: Start of data availability (01 January 2016) to the end of data

MM diagnosis window: Start of data availability (01 January 2016) to index date

Index date: First elranatamab claim after initial MM diagnosis

Observability: At least 180 days of continuous closed-claims medical and pharmacy enrollment prior to index (inclusive)

[figure not shown]
Baseline period for MM-related treatments and MM-related comorbidities: MM diagnosis to one day prior to index date (unless otherwise specified)

CCI and baseline HCRU assessment window: 180 days prior to index date to index date.

Follow-up: Index date until death, the earliest of the end of data, or end of continuous enrollment (unless otherwise noted). Alternative censoring criteria will be applied for certain outcomes (such as OS, TTD, and TTNT/D); see [Section 9.7](#) for more details.

Figure 1 reflects the time periods of interest in the study cohort.

Figure 1. Study Schematic for Patients Receiving Elranatamab

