9.3. Variables

Table 1 includes definitions and assessment periods for all study variables that will be used as eligibility criteria. The full code list can be found in ANNEX 2. ADDITIONAL INFORMATION.

Table 1. Variables Used to Determine Eligibility

Variable	Operational Definition	Role	Assessment Period
Elranatamab	Prescription claim or medical claim with a National Drug Code (NDC), Healthcare Common Procedure Coding System (HCPCS), ICD-10 code or generic name in the IP, non-IP or pharmacy setting for elranatamab	Inclusion	Index event
Teclistamab	Prescription claim or medical claim with an NDC, HCPCS, ICD-10 code or generic name in the IP, non-IP or pharmacy setting for teclistamab	Exclusion	All available data to index date

Variable	Operational Definition	Role	Assessment Period
Age	Age is greater than or equal to 18 years and is not missing	Inclusion	Index date
MM diagnosis	Medical claim in the IP or non-IP setting with an ICD-10 code for MM	Inclusion	All available data to index date
Observability	Closed-claims medical and pharmacy enrollment	Inclusion	180 days prior to index date to index date (inclusive)

Table 2 includes definitions and assessment periods for all study variables that will be used as baseline and treatment characteristics. The full code list can be found in ANNEX 2.
 ADDITIONAL INFORMATION. If applicable, the frequency and percentage of patients with missing data for each variable will be described.

Table 2. Variables Used to Determine Baseline and Treatment Characteristics

Objective	Variable	Definition	Assessment Period(s)
1	Age	Age in years (continuous)	Index date
1	Sex	Categorical sex Male Female	Index date
1	Race/Ethnicity	Categorical race and ethnicity Caucasian African American Asian or Pacific Islander Hispanic or Latino Other	Start of data availability to index date

Objective	Variable	Definition	Assessment Period(s)
		Unknown	
1	Region	Categorical region, assessed as the most recent value from index date Northeast Midwest West South	Start of data to index date
	Insurance type	Categorical insurance type, assessed as the most recent value to index date Commercial Medicaid Medicare Other Unknown	180 days prior to index date to index date
1	Location (Zip code)	Categorical zip code assessed as the most recent value from index date. The full categories will be reported during implementation.	Index date
1	Care setting	Categorical care setting for elranatamab or teclistamab administration IP Non-IP Pharmacy	Index date

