ANNEX 2. ADDITIONAL INFORMATION

Variable	Role	Data Source(s)	Codes	Source
Elranatamab	Inclusion criteria	Claims data	HCPCS: C9165, J1323 NDC: 00069449401, 00069449402, 00069252201, 00069252202 ICD-10 Procedure code: XW013L9 Generic name: Elranatamab	ELREXFIO Outpatient Billing (2024) ELREXFIO Inpatient Billing (2024)
Teclistamab	Inclusion criteria (Exploratory cohort)	Claims data	HCPCS (Mapped via SEER using generic name): J9380, C9148 NDC: 57894044901, 57894045001 ICD-10 Procedure code: XW01348 Generic name: Teclistamab	Janssen Biotech (2023) SEER (2024)
Multiple Myeloma	Inclusion criteria, Outcome - HCRU	Claims data	C90.0x	ELREXFIO Outpatient Billing (2024)
Age	Inclusion criteria, Baseline characteristic - Demographic	Claims data	N/A	N/A
Sex	Baseline characteristic - Demographic	Claims data	N/A	N/A
Race/Ethnicity	Baseline characteristic - Demographic	Claims data	N/A	N/A

PFIZER CONFIDENTIAL

Redacted

Insurance type	Baseline characteristic - Demographic	Claims data	N/A	
Care setting	Baseline characteristic - Clinical	Claims data	See rows below: "Inpatient," "Outpatient," and "Emergency Department"	N/A
Hematopoietic stem cell transplantation	Baseline characteristic - Treatments	Claims data	
CPT: 38240, 38241, 38242, 38243
 
ICD-10 Diagnosis: T86.0, T86.00, T86.01, T86.02, T86.03, T86.09, T86.5, Z48.290, Z94.81
 
ICD-10 Procedure: 30240Y0, 30243Y0, 30250Y0, 30253Y0, 30260Y0, 30263Y0, 30230Y1, 30233Y1, 30240Y1, 30243Y1, 30230Y2, 30233Y2, 30240Y2, 30243Y2, 30230Y3, 30233Y3, 30240Y3, 30243Y3, 30230Y4, 30233Y4, 30240Y4, 30243Y4, 30253Y1, 30260Y1, 30263Y1, 30233X0, 30233G0, 30233G1, 30233G2, 30233G3, 30233X1, 30233X2, 30233X3, 30233X4, 30233Y0, 30243X0, 30243G0, 30243G1, 30243G2, 30243G3, 30243X1, 30243X2, 30243X3, 30243X4, 0243Y4, 30283X0, 30283G0, 30283G1, 30283G2, 30283G3, 30283X1, 30283X2, 30283X3, 30283X4, 30283Y1, 30283Y2, 30283Y3, 30283Y4
	
Chaudhry et al. (2022)
 
LeMaistre et al. (2013)

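### The Annex 2 code list for prior stem cell transplant has the bone-marrow status code but not the stem-cell status code, so baseline HSCT may be under-counted by an unknown amount (minor)

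*Protocol*

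**What the plan says.** Section 9.3, Table 2, lists HSCT under Objective 1 as a dichotomous variable: "Medical claim with an HCPCS, CPT, or ICD-10 code for hematopoietic stem cell transplantation in the IP, non-IP setting (dichotomous". It is assessed twice, from MM diagnosis to the day before index and again from index to the end of follow-up. For the codes the section sends the reader to the annex: "The full code list can be found in ANNEX 2".

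The HSCT row in Annex 2 has procedure codes ("CPT: 38240, 38241, 38242, 38243" and a long list of ICD-10 procedure codes) and nine ICD-10 diagnosis codes: "T86.0, T86.00, T86.01, T86.02, T86.03, T86.09, T86.5, Z48.290, Z94.81". Z94.84 is not among them and does not appear elsewhere in the protocol.

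Section 9.2 sets the time frame. Baseline for MM treatments is "MM diagnosis to one day prior to index date (unless otherwise specified". The data begin in 2016: "MM diagnosis window: Start of data availability (01 January 2016) to index date". The enrollment requirement is "At least 180 days of continuous closed-claims medical and pharmacy enrollment prior to index (inclusive".

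The row serves the first primary objective: "Describe the demographics, clinical history, and treatment history of patients in the study".

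**The concern.** The diagnosis list is uneven. On the bone-marrow side it has complication codes (T86.0 and its subcodes) and the status code (Z94.81). On the stem-cell side it has the complication code (T86.5) but no status code. A variable named for stem cell transplantation thus accepts a record of past bone-marrow transplant and does not accept the equivalent record of past stem cell transplant. The protocol gives no reason for the difference.

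At stake is the accuracy of one treatment-history percentage in the baseline table of each cohort. An uncomplicated transplant whose procedure claim is not in the data, and which is recorded later only under Z94.84, would be reported as no transplant.

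**Working it through.** The plan states no figure here, so there is nothing to reproduce. The check has four steps.

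**1. Membership of the code list.** The nine diagnosis codes in Annex 2 are six in the T86.0 group (T86.0, T86.00, T86.01, T86.02, T86.03, T86.09), plus T86.5, Z48.290 and Z94.81: 6 + 1 + 1 + 1 = 9. The only Z94 code is Z94.81. The protocol does not print code meanings. Those used here come from ICD-10-CM, the code set the protocol applies, and one look-up verifies them. The annex is consistent with Z94.x being transplant-status codes: it uses Z94.0 under renal disease and Z94.4 under liver disease.

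**2. Direction.** The variable is yes if at least one listed code appears. Adding a code to the list can turn a no into a yes but never the reverse. The effect of leaving out a valid code is therefore downward or nil.

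**3. Who is missed.** A patient is wrongly scored no because of this omission only if all of the following hold between MM diagnosis and the day before index:
- no listed CPT or ICD-10 procedure code on any claim;
- none of the nine listed diagnosis codes on any claim;
- at least one claim with Z94.84.

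This can happen when the transplant came before 01 January 2016 or fell outside captured claims.

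**4. Size, as illustration only.** Let p be the true proportion with prior HSCT, h the share of those known only from history codes, and m the share of that group whose only code is Z94.84. Then

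reported proportion = p × (1 − h × m), and loss = p × h × m.

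All three inputs are assumptions, because the documents give none of them.

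- Low: p = 0.40, h = 0.10, m = 0.25. Loss = 0.40 × 0.10 × 0.25 = 0.010, or 1 point (39% reported against 40%).
- Middle: p = 0.60, h = 0.30, m = 0.50. Loss = 0.60 × 0.30 × 0.50 = 0.090, or 9 points (51% against 60%).
- High: p = 0.70, h = 0.50, m = 0.90. Loss = 0.70 × 0.50 × 0.90 = 0.315, or about 32 points (38.5% against 70%).

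To give a scale in patients, section 9.5 counts 56 with an elranatamab claim. In the middle case that is 56 × 0.60 = 33.6 true against 56 × 0.51 = 28.6 reported, about five patients. The 56 is a count of patients with a claim, not of the analysed cohort, and it will change with the refreshes.

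**The case against.** The strongest reply is that little may be lost. The look-back for this variable is not 180 days. That figure is a minimum for closed-claims enrollment, while the HSCT window runs from MM diagnosis. From the data start to the earliest possible index date, 14 August 2023, is about 7.6 years, and the source includes open as well as closed claims. A patient must slip past every procedure code and all nine diagnosis codes over that whole window. This stands, and it is why the size may be small. It does not remove the gap: a procedure before 2016 has no claim in the data, and completeness before the 180 days is not assured.

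A second reply is that the meaning of Z94.84 is not in the protocol, and that the list is attributed to two publications not available here, so the omission may be inherited rather than a slip. It is true that intent cannot be known. The absence of the code is nevertheless plain in Annex 2, and inheriting a list would not make it complete for this variable.

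A third reply is that the limitations section already concedes misclassification. It speaks of provider coding and data-entry errors, not of a gap in the study's own list.

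A reader might go further and infer that the diagnosis codes were included on purpose to recover past transplants, or that the status code is often the only trace of one. The protocol states neither. A reader might also infer a biased contrast between the elranatamab and teclistamab cohorts. That would require their look-back or coding to differ, which the documents do not show, and section 9.7 plans no formal comparison between groups.

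**Conclusion.** The point holds in a limited form. Annex 2 omits the stem-cell transplant status code while listing the bone-marrow one, and the effect of this omission on the baseline HSCT percentage can only be downward. This rests on the ICD-10-CM meanings of Z94.81 and Z94.84 and on the any-code definition in Table 2.

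The size is unknown. The spread of about 1 to 32 points comes wholly from assumed inputs and should not be quoted as an estimate. The supported statement is that prior HSCT may be understated, not that it is understated by a material amount.

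The severity is minor. HSCT is one descriptive baseline row. It is not an eligibility criterion, it is not in the next-treatment definition used for time to discontinuation or for time to next treatment or death, and it triggers no censoring.

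**What to change.** In the HSCT row of Annex 2, add Z94.84 to the ICD-10 diagnosis codes and mark it for the baseline window only, from MM diagnosis to one day before index. Do not use it to identify transplants from index onward, because a status code there can record an old transplant as a new one. If the code was left out on purpose, state the reason in the annex instead.

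Re-run the baseline HSCT row for both cohorts at the next refresh. At the date of protocol version 2.0 (31 July 2025), refreshes 3 and 4 and the final report were still ahead. Version 2.0 itself corrected an annex list in a similar way, by adding MM codes to a comorbidity component.

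The cost is one added code and one re-run table row, with no new data. The reported percentage may shift from earlier refreshes, so the row should carry a note saying that the code list changed.
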